8.9. Renal Endpoint Analyses

The following endpoints will be evaluated in the Renal Evaluable Population.

8.9.1. Best Renal Response from Baseline

Best renal response will be analyzed in the same manner described [Section 8.6.1](#).

8.9.2. Renal Response at Each Visit

Renal response at each visit will be analyzed in the same manner described [Section 8.6.1](#) .

8.9.3. Creatinine, Proteinuria and eGFR: Change from Baseline

Change from baseline in creatinine, proteinuria and eGFR will be analyzed in the same manner described in [Section 8.6.3](#).

8.10. Peripheral Neuropathy Endpoint: Change from Baseline in NIS-LL Total Score

Change from baseline in NIS-LL will be evaluated in the Peripheral Neuropathy Evaluable Population, in the same manner described in [Section 8.6.3](#).

8.11. All-Cause Mortality (Overall Survival)

Overall survival, time to all-cause mortality, will be calculated in days as the date of death minus the date of first NEOD001 infusion plus 1. Subjects will be censored at their last assessment known to be alive prior to LSLV. Refer to [Section 8](#) for details about course of the study and relative first infusion of study drug for each set of analysis.

Kaplan-Meier (KM) estimates of the distribution of the time-to-event will be tabulated. The tabulation will include the KM estimate of the medians, 25th and 75th quartiles, and corresponding 95% CIs, if estimable. The number and percent of subjects censored and with events will be presented.

8.12. Other Efficacy Data

Below efficacy data will be presented in by-subject data listings for the OLE Safety Population.

- Visual Analog Scale – Pain Intensity (VASPI)
- Kansas City Cardiomyopathy Questionnaire (KCCQ)
- Eastern Cooperative Oncology Group (ECOG) performance
- Free light chains (sFLCs), serum and 24-hour urine protein electrophoresis (PEP), and serum and urine immunofixation electrophoresis (IFE)
- Severity of disease-related symptoms including any changes from baseline
- Pharmacokinetics (PK)

9. SAFETY ANALYSES

All recorded safety endpoint data will be presented in by-subject data listings for the OLE Safety Population. TEAE summaries will be presented for All Treated Subjects. Extent of exposure will be summarized for NEOD001 Safety Population and OLE Safety Population.

No inferential comparison of safety endpoints will be performed.

9.1. Extent of Exposure

The total patient exposure years (PEY) for each subject is defined as the time interval between the first dose and the last dose, inclusive, of study drug based on the subject's study drug administration information. One PEY is the equivalent of 1 subject exposed to study drug for 1 year. Two subjects who are exposed to study drug for half a year together contribute one PEY. The total PEY is the sum of the person exposure years of each subject in that treatment group. Duration of exposure is defined in days as the date of the last infusion of study drug – the date of the first infusion of study drug + 1.

Study drug exposure summaries will include:

- The number of subjects exposed to NEOD001, the total PEY, and duration of exposure will be summarized using descriptive statistics.
- Total Number of Infusions received will be determined for each subject by number of times the start time of drug infused is reported. If multiple infusion start times are reported on a single day, then only 1 infusion will be counted for that day. If the start time of drug infused is missing but total volume infused is greater than 0 mL, 1 infusion will be counted for that day. The number of infusions received will be summarized using descriptive statistics. In addition, cumulative number of subjects receiving infusions at each visit will be presented.

All recorded and derived exposure data will be presented in a by-subject data listing.

9.2. Use of Premedication

Subjects may be premedicated with 25 mg diphenhydramine (or an equivalent dose of a H1 antihistamine) and 650 mg acetaminophen (or an equivalent paracetamol dose) within 30-90 minutes prior to study drug administration. Premedications will be mapped to Anatomical Therapeutic Chemical (ATC) class and Preferred Name using the WHO Drug Dictionary, B2 Enhanced December 2015.

Premedication data will be presented in a by-subject data listing.

9.3. Adverse Events

Verbatim terms on the OLE Adverse Event eCRFs will be mapped to PT and SOC using MedDRA version 19.0. AEs will be reported, and severity will be categorized using the Common Terminology Criteria for Adverse Events (CTCAE, Version 4.03).

All AE summaries will be restricted to treatment-emergent adverse events (TEAEs), which are defined as any AE that newly appears, increases in frequency, or worsens in severity following initiation of study drug and up to 30 days after date of last dose or last study visit, whichever is

later. If it cannot be determined whether the AE is treatment emergent due to a partial onset date, then it will be counted as such.

To assess the long-term treatment effects overall and relative to shorter term treatment, TEAE incidence will be summarized separately by the original parent study (NEOD001-201) and OLE study (NEOD001-OLE251) as shown in Table 6. TEAEs collected during original parent study will be summarized by actual treatment subjects received. TEAEs that start on or after the first dose of OLE study will be summarized by treatment group subjects received in parent study. Overall summary will also be presented for NEOD001-OLE251.

Table 6: Treatment Group Schema

NEOD001-201		NEOD001-OLE251		
NEOD001 (N=xx)	Placebo (N=xx)	NEOD001-201 NEOD001 (N=xx)	NEOD001-201 Placebo (N=xx)	Overall (N=xx)

Each AE summary will be presented according to Table 6 for All Treated Subjects. Summaries that are displayed by SOC and PT will be ordered by descending order of NEOD001-OLE251 overall incidence of SOC and PT within each SOC.

- An overall summary of AE incidences will be presented, including the number and percent of subjects with at least one of:
 - Any TEAE
 - TEAE by maximum CTCAE Grade
 - CTCAE Grade ≥ 3 TEAE
 - Serious TEAE
 - Fatal TEAEs (outcome="Fatal" or severity=CTCAE Grade 5)
 - Treatment-related TEAE
 - Treatment-related serious TEAE
 - Treatment-related TEAE of CTCAE \geq Grade 3
 - TEAE leading to infusion interruption
 - TEAE leading to dose reduction
 - TEAE leading to dose being held
 - TEAE leading to prolongation of infusion time (>2.5 hours)
 - Infusion associated TEAE as determined by the Investigator
 - TEAE leading to study drug withdrawal
- Subject incidence of TEAEs by MedDRA SOC and PT
- Subject incidence of serious TEAEs by MedDRA SOC and PT

The following listings will be presented by subject for OLE Safety Population:

- All AEs
- SAEs (this is a subset of the AEs where serious is marked as “Yes”)
- AEs leading to Study Drug Withdrawal (this is a subset of the AEs where Action Taken with Study Treatment is checked as “Drug Discontinued”)
- AEs leading to death (this is a subset of the AEs where outcome is indicated as “Fatal” or the CTCAE grade is 5)

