4 SELECTION, DISCONTINUATION, AND WITHDRAWAL OF SUBJECTS

4.1 Inclusion Criteria

Subjects must meet *all* of the following criteria:

1. Completed the EOS Visit in Study NEOD001-201
2. Adequate bone marrow reserve, hepatic and renal function, as demonstrated by:
 - Absolute neutrophil count (ANC) $\geq 1.0 \times 10^9/L$
 - Platelet count $\geq 75 \times 10^9/L$
 - Hemoglobin ≥ 9 g/dL
 - Total bilirubin $\leq 2 \times$ upper limit of normal (ULN)
 - Aspartate aminotransferase (AST) $\leq 3 \times$ ULN
 - Alanine aminotransferase (ALT) $\leq 3 \times$ ULN
 - Alkaline phosphatase (ALP) $\leq 5 \times$ ULN (except for subjects with hepatomegaly and isozymes specific to liver, rather than bone)
 - Estimated glomerular filtration rate (eGFR) ≥ 25 mL/min/1.73 m² as estimated by the Chronic Kidney Disease Epidemiology Collaboration (CKD-EPI) equation, or measured GFR ≥ 25 mL/min/1.73 m²
3. Systolic blood pressure (BP) 80-180 mmHg
4. Women of childbearing potential (WOCBP) must have a negative pregnancy test during Screening and must agree to use highly effective physician-approved contraception ([Appendix 2](#)) from Screening to 90 days following the last study drug administration
5. Male subjects must be surgically sterile or must agree to use highly effective physician-approved contraception ([Appendix 2](#)) from Screening to 90 days following the last study drug administration
6. Ability to understand and willingness to sign an informed consent form (ICF) prior to initiation of any study procedures

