 - Major surgery within 4 weeks (or within 2 weeks following consultation with and approval of Medical Monitor)
 - Planned organ transplant during the study
 - Any investigational agent, other than NEOD001, within 4 weeks

- Any experimental imaging agent directed at amyloid within 2 years
8. Active malignancy *with the exception* of any of the following:
 - Adequately treated basal cell carcinoma, squamous cell carcinoma, or in situ cervical cancer
 - Adequately treated Stage I cancer from which the subject is currently in remission and has been in remission for ≥ 2 years
 - Low-risk prostate cancer with Gleason score < 7 and prostate-specific antigen < 10 mg/mL
 - Any other cancer from which the subject has been disease-free for ≥ 2 years
 9. History of Grade ≥ 3 infusion-related AEs or hypersensitivity to NEOD001
 10. History of severe allergy to any of the components of NEOD001 such as histidine/L-histidine, Trehalose, or Polysorbate 20
 11. Currently known uncontrolled bacterial, viral, fungal, HIV, hepatitis B, or hepatitis C infection
 12. Women who are breastfeeding
 13. Any condition which could interfere with, or the treatment for which might interfere with, the conduct of the study or which would, in the opinion of the Investigator, unacceptably increase the subject's risk by participating in the study
 14. Unable or unwilling to adhere to the study-specified procedures and restrictions
 15. Subject is under legal custodianship

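### SAP Table 6 compares long-term with shorter-term TEAE incidence in different sets of subjects over unequal follow-up, with no like-for-like parent-study column

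*SAP*

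**What the plan says.** SAP 9.3 states why parent and OLE events are tabulated side by side: "To assess the long-term treatment effects overall and relative to shorter term treatment, TEAE incidence will be summarized separately by the original parent study". It then sets out the columns.

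- Population: "Each AE summary will be presented according to Table 6 for All Treated Subjects". SAP 9 says the same: "TEAE summaries will be presented for All Treated Subjects". SAP 5 does not define this population. Because SAP 9.3 names the OLE Safety Population separately for its listings, the natural reading is everyone dosed in the parent study.
- Parent columns: "TEAEs collected during original parent study will be summarized by actual treatment subjects received". No restriction to OLE entrants is stated.
- OLE columns: "TEAEs that start on or after the first dose of OLE study will be summarized by treatment group subjects received in parent study". An overall OLE column is added.
- Measure: counts and percentages of subjects with one or more events. SAP 9.1 derives exposure years, but nothing ties them to the TEAE tables.

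Entry to the OLE is conditional. Protocol 4.1 requires, as its first criterion, "Completed the EOS Visit in Study NEOD001-201", and sets laboratory and systolic blood pressure limits. Protocol 4.2 excludes new clinically significant abnormalities that preclude treatment or participation (criterion 1). It also excludes a history of Grade 3 or higher "infusion-related AEs or hypersensitivity to NEOD001" (criterion 9).

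**The concern.** The two sides of the contrast hold different people. Anyone who died in the parent study, left it early, or failed OLE screening counts in the parent columns and cannot count in the OLE columns. Part of that filter acts on outcomes that Table 6 reports. Survival to the parent end-of-study visit bears on the fatal row, and criterion 9 bears on the infusion-associated row. A difference between parent and OLE percentages can therefore arise with no change in any subject's risk.

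This matters more than usual because SAP 10 removes all safety analyses except the AE overview, TEAEs and SAEs. Table 6 is then the main remaining safety summary, and long-term safety is half of the study objective. A reader who uses the table for its stated purpose has no same-subject reference to turn to.

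**Working it through.** The documents give no TEAE rate, rollover rate or sample-size figure, so there is no stated result to reproduce. The check has three parts: follow-up from the documents, then selection and duration under assumed rates.

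**Follow-up.** SAP Table 2 puts the parent end-of-study visit at target Day 338. SAP 2.2.1 allows up to 36 infusions every 28 days in the OLE. With 30 days after the last dose, the maximum is (36 − 1) × 28 + 1 + 30 = 1011 days, and 1011 / 338 = 2.99. Actual OLE follow-up is not given, and the program was discontinued (SAP 10).

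**Selection at equal follow-up.** Assume two risk classes, a constant first-event rate λ within each, and no effect of drug or time. Follow-up T is 338 / 365.25 = 0.925 years, and half of that in the parent study for subjects who do not enter the OLE. The risk of an event by T is 1 − exp(−λT).

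Middle scenario: 25% high risk, rates of 2.0 and 0.3 per year, OLE entry 50% and 95%.

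- Risks at full T: 84.3% and 24.2%. Risks at half T: 60.4% and 13.0%.
- Parent, all treated: 0.25 × (0.5 × 84.3 + 0.5 × 60.4) + 0.75 × (0.95 × 24.2 + 0.05 × 13.0) = 35.8%.
- OLE entrants: (0.125 × 84.3 + 0.7125 × 24.2) / 0.8375 = 33.2%.
- Gap: 2.6 points.

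All five scenarios (every rate and entry share is an assumption):

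| High-risk share | Rates per year (high / low) | Entry (high / low) | Parent, all treated | OLE entrants at 338 days | Gap (points) | Break-even OLE follow-up (days) |
|---|---|---|---|---|---|---|
| 25% | 2.0 / 0.3 | 50% / 95% | 35.8% | 33.2% | 2.6 | 379 |
| 25% | 1.5 / 0.3 | 50% / 95% | 33.4% | 31.8% | 1.6 | 361 |
| 25% | 2.0 / 0.3 | 70% / 95% | 37.0% | 36.1% | 0.9 | 352 |
| 10% | 2.0 / 0.3 | 50% / 95% | 28.5% | 27.6% | 0.9 | 354 |
| 25% | 3.0 / 0.2 | 30% / 95% | 32.5% | 24.2% | 8.3 | 539 |

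A simpler illustration assumes that 70% of non-entrants and 30% of entrants have a serious TEAE over an equal period. With 20% not entering, the parent column shows 0.2 × 70 + 0.8 × 30 = 38% against 30% in the OLE, a gap of 8 points. With 10% or 30% not entering, it shows 34% or 42%, gaps of 4 or 12.

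Restricting the parent columns to OLE entrants gives 33.2% in the middle scenario, equal to the OLE figure at 338 days, so the gap closes. This equality is built into the model, which selects on risk class and not on the event itself. It does not carry over to rows where entry depends directly on the event.

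**Duration.** In the middle scenario, OLE crude incidence is 11.9% at 90 days, 21.0% at 180, 33.2% at 338, 42.6% at 500 and 62.9% at 1011, against 35.8% in the parent column. The OLE looks safer only up to about 379 days (352 to 539 across scenarios). With no selection at all and 0.5 events per year in everyone, incidence is 37.0% at 338 days, 21.8% at 180 and 74.9% at 1011.

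**The case against.** The strongest reply is that the direction is not established. A reader might infer that long-term treatment will look safer through selection alone. The documents do not support that. Table 6 shows crude percentages over follow-up that may be shorter or about three times longer than in the parent study. Duration alone can move the contrast either way and by more than selection does. The OLE also allows concomitant chemotherapy (SAP 2.2.1), whereas the parent study tested a single agent in stable plasma cell disease (Protocol 1.3), which may raise OLE incidence. This objection stands, and it limits the point to a contrast that cannot be interpreted as planned.

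Second, same-subject parent columns bring a bias of their own. Entrants are chosen partly on parent-study outcome, so in the rows tied to entry any OLE event would look like worsening. This also stands, and it is why the restricted columns should not be the sole reference.

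Third, former-placebo subjects had no NEOD001 in the parent study, so they were not selected on tolerating it. They enter the overall OLE column at first exposure. This is correct and bears on which pair of columns to read.

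Fourth, SAP 9 rules out inferential safety comparison, each column carries its own N, and SAP 7.1 tabulates parent-dosed, screened and enrolled counts. This makes attrition visible and means that no test is at risk. It does not supply the missing same-subject column, and a descriptive table with a stated comparative purpose will still be read comparatively.

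**Conclusion.** The point holds in limited form. Table 6 cannot serve its stated purpose as planned, because it compares all parent-treated subjects with a screened subset of completers, by crude incidence over unequal time. Selection taken alone lowers the OLE columns. Its size is assumed, not documented: about 1 to 8 points in the scenarios and 4 to 12 in the simpler illustration, both at equal follow-up. The net direction in the actual table is unknown. Fixing selection without follow-up, or follow-up without selection, leaves the contrast confounded.

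The conclusion assumes that *All Treated Subjects* means everyone dosed in the parent study. The numbers of parent-study deaths, withdrawals and non-entrants are not given. The consequence is a misleading descriptive reading, not a false test result, and the remedy is a cheap improvement.

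**What to change.** - In SAP 5, define *All Treated Subjects* as all subjects dosed in the parent study.
- In Table 6, keep the all-treated parent columns and add two parent-study columns restricted to the OLE Safety Population, by actual parent treatment.
- Show exposure-adjusted or equal-interval incidence beside the crude percentages, using the exposure data derived in SAP 9.1. State the denominator: exposure years in SAP 9.1 stop at the last dose, while the TEAE window runs at least 30 days beyond it.
- For any long-term versus shorter-term statement, use former-NEOD001 subjects' restricted parent column against their OLE column as the main pair. The overall OLE column mixes first and continued exposure.
- Footnote that fatal TEAEs in the restricted parent columns are zero by design, and that Grade 3 or higher infusion-related events and drug withdrawals are lowered there by the OLE entry criteria. Those rows must not be read as a change over time from the restricted columns alone.

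The cost is two columns and one added measure, from data that Table 6 and SAP 9.1 already use. The downside is a wider table that needs the footnotes above. Chemotherapy in the OLE remains a limitation to state in the text.

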4.6.1. PRONTO Visit Windows

PRONTO visit windows, as defined in PRONTO SAP, will be used to map the data collected in parent study (NEOD001-201).

[Table 2](#) defines the visit windows for assessments taken at 1-month intervals to be established with respect to relative day from the start of study drug in parent study.

Table 2: PRONTO 1-Month Interval Visit Windows (Days)

Months	Target Study Day ^a	Analysis Window Study Day ^a	
		Low	High
PRONTO Baseline ^b	1	Closest visit to Day 1, prior to first NEOD001 dose	
PRONTO Month 2	28	14	42
PRONTO Month 3	56	43	70
PRONTO Month 4	84	71	98
PRONTO Month 5	112	99	126
PRONTO Month 6	140	127	154
PRONTO Month 7	168	155	182
PRONTO Month 8	196	183	210
PRONTO Month 9	224	211	238
PRONTO Month 10	252	239	266
PRONTO Month 11	280	267	294

Months	Target Study Day ^a	Analysis Window Study Day ^a	
		Low	High
PRONTO Month 12	308	295	319 [EEOS Low – 1]
PRONTO EEOS ^c	338	320 [Month 12 Low + 30 – 5]	

^a Study day will be calculated from first dose date in parent study.

^b PRONTO Baseline is defined in Section 2.2.4.

^c PRONTO EEOS is defined as the visit occurring 30 (-5) days after the Month 12 infusion in parent study.

Table 3 defines the visit windows for assessments taken at 3-month intervals to be established with respect to relative day from the start of study drug in parent study.

Table 3: PRONTO 3-Month Interval Visit Windows (Days)

Months	Target Study Day ^a	Analysis Window Study Day ^a	
		Low	High
PRONTO Baseline ^b	1	Closest visit to Day 1, prior to first NEOD001 dose ^b	
PRONTO Month 3	56	14	98
PRONTO Month 6	140	99	182
PRONTO Month 9	224	183	266
PRONTO Month 12	308	267	319 [EEOS Low – 1]
PRONTO EEOS ^c	338	320 [Same definition as table 3]	

^a Study day will be calculated from first dose date in parent study.

^b PRONTO Baseline is defined in Section 2.2.4.1

^c PRONTO EEOS is defined as the visit occurring 30 (-5) days after the Month 12 infusion in parent study.

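### SAP 9.3 sets long-term against shorter-term safety using crude TEAE percentages from periods of unequal length, with no person-time defined for the Table 6 columns

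*SAP*

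**What the plan says.** **Purpose and measure.** SAP 9.3 introduces the tables with "To assess the long-term treatment effects overall and relative to shorter term treatment, TEAE incidence will be summarized separately by the original parent study" and, alongside it, by the OLE. Table 6 has five columns: NEOD001 and placebo in the parent study, then the OLE split by parent arm, then OLE overall. For the OLE columns, "TEAEs that start on or after the first dose of OLE study will be summarized by treatment group subjects received in parent study". The overview table is a count of subjects, "including the number and percent of subjects with at least one of" a list of event types. The tables by system organ class and preferred term are also subject incidence. No rate, time to first event or period-matched summary is planned.

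**Event window.** TEAEs are counted from the start of study drug "and up to 30 days after date of last dose or last study visit", taking the later of the two.

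**Exposure.** Under SAP 9.1 a subject's PEY "is defined as the time interval between the first dose and the last dose, inclusive, of study drug". SAP 9 adds: "Extent of exposure will be summarized for NEOD001 Safety Population and OLE Safety Population". The TEAE tables use a different set, All Treated Subjects, which SAP Section 5 does not define. SAP Section 10 then says that only the AE overview, TEAEs and SAEs survive among the safety analyses; exposure is not named there.

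**Period lengths.** SAP Table 2 puts parent Month 12 at target Day 308 and EEOS at Day 338: "PRONTO EEOS is defined as the visit occurring 30 (-5) days after the Month 12 infusion in parent study". SAP 2.2.1 allows up to 36 OLE infusions at 28-day intervals. Section 10 records that the program was discontinued. Neither document gives the OLE duration actually reached.

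**The concern.** The percentage of subjects with at least one event rises as follow-up lengthens, even when risk per month does not change. Parent and OLE columns placed side by side for a long-term versus shorter-term reading therefore mix risk with length of observation. Long-term safety is half of the study's single objective, and Section 10 leaves the AE tables as the main safety summaries. A reader could see a worse or better long-term profile where risk is the same.

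The natural remedy is to divide by exposure, but the exposure figure in 9.1 was not built for that. It is planned for two populations rather than for the five columns, so the parent columns, and the parent placebo column in particular, have no matching denominator. It also ends at the last dose, while events continue to be counted afterwards.

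**Working it through.** **Inputs from the documents.** Infusions every 28 days; 12 parent infusions; up to 36 OLE infusions; TEAE window at least 30 days past the last dose; PEY from first to last dose, inclusive.

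**Assumptions (not in the documents).** A constant hazard, equal in both studies; the 20% incidence; the hazard values; the OLE infusion counts; the gaps between studies.

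**1. Reproduce the plan's own figures.** 28 × 11 = 308 and 308 + 30 = 338, matching SAP Table 2. 1 + 36 + 1 = 38 months, matching the maximum participation in Protocol 3.6.

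**2. Period lengths.** For k infusions, PEY days = 28(k − 1) + 1 and the minimum TEAE window = PEY days + 30. The last column is the factor by which a rate based on PEY would be overstated.

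| Infusions k | PEY days | TEAE window, days | Window ÷ PEY |
|---|---|---|---|
| 3 | 57 | 87 | 1.53 |
| 6 | 141 | 171 | 1.21 |
| 12 | 309 | 339 | 1.10 |
| 24 | 645 | 675 | 1.05 |
| 36 | 981 | 1011 | 1.03 |

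The parent window of 339 days is 339/30.4375 = 11.1 months. The longest OLE window is 1011/30.4375 = 33.2 months.

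**3. What a 20% parent incidence becomes.** Percentage after m months = 1 − (1 − 0.20)^(m/11.1).
- m = 6: 1 − 0.8^0.541 = 11%
- m = 24: 1 − 0.8^2.162 = 38%
- m = 33.2: 1 − 0.8^2.991 = 49%

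**4. The same effect over a range of hazards.** Percentage = 1 − exp(−hazard × window/365.25).

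| First events per person-year | Parent, 12 infusions | OLE, 36 infusions | OLE, 6 infusions |
|---|---|---|---|
| 0.1 | 8.9% | 24.2% | 4.6% |
| 0.25 | 20.7% | 49.9% | 11.0% |
| 0.5 | 37.1% | 74.9% | 20.9% |
| 1.0 | 60.5% | 93.7% | 37.4% |

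Risk is identical across each row, yet the OLE looks worse with long follow-up and better with short follow-up.

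**5. With the proposed denominator.** Use time from first dose in that study to first event or end of its TEAE window. At a hazard of 0.5, the expected first-event rate is 0.5 per person-year in every column, whatever the follow-up.

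**6. Conditional check: PEY pooled over both studies.** If parent and OLE dosing were joined, pooled PEY = 309 + 30 + gap + 28(k − 1) + 1, where the gap runs from last parent visit to first OLE dose. The sum of the two TEAE windows = 339 + 28(k − 1) + 31. The ratio of windows to pooled PEY, for gaps of 0, 60, 180 and 365 days, is:
- k = 6: 510/480 = 1.06; 510/540 = 0.94; 510/660 = 0.77; 510/845 = 0.60
- k = 36: 1350/1320 = 1.02; 1350/1380 = 0.98; 1350/1500 = 0.90; 1350/1685 = 0.80

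Stopping at the last dose overstates a rate and counting the gap understates it, so the two would partly offset each other.

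**The case against.** **The table is descriptive.** SAP 9 rules out inferential comparison of safety endpoints. SAP 9.1 plans duration, infusion counts, cumulative subjects infused by visit and by-subject listings, all of which give context. That is fair, but the descriptive comparison is the declared purpose of the table, and Section 10 leaves it unclear whether the exposure summaries will be produced.

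**PEY was meant to describe exposure.** It is not offered as an AE denominator. On OLE data alone its error is 3% at 36 infusions and 10% at 12. This stands: it would be wrong to say that PEY is useless for the OLE columns. The weakness is serious only for short courses, and the parent columns remain without a denominator.

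**Does PEY count the gap between studies?** A reader might infer so from first dose to last dose. The documents do not support it as a fact. SAP 9.1 does not say that the two dosing periods are joined. The only pooling rule is in Section 8, for efficacy, and it restricts the OLE Safety Population to OLE data. The gap would enter only for the NEOD001 Safety Population, and only if that rule were carried into 9.1.

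**Does PEY count placebo time?** A reader might infer this too. SAP Section 5 defines the NEOD001 Safety Population as subjects given NEOD001 in the parent study, which excludes parent-placebo subjects. Section 8 lists a placebo group within that population, which conflicts with Section 5 but does not show that placebo time is counted as exposure.

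**Rates would not make the columns comparable.** OLE subjects had completed the parent study (Protocol 4.1), and a history of Grade 3 or higher infusion-related events excluded them (Protocol 4.2). This selection stands and limits what any adjustment can achieve. It does not justify leaving follow-up length uncorrected as well.

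**Conclusion.** The point holds for the parent-versus-OLE reading of Table 6. Crude percentages over unequal periods do not serve the stated purpose, and no person-time is defined for the columns. Under a constant hazard, follow-up length alone could turn 20% into anything from about 11% (6 months) to 49% (33 months). These figures illustrate sensitivity; they do not predict the result. It would go too far to say that the comparison mainly reflects duration or that the OLE will look worse: actual OLE duration is not given, so neither the size nor the direction of the distortion is known.

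On exposure, the supported conclusion is narrower: PEY is not defined by Table 6 column, it stops at least 30 days before the TEAE window closes, and SAP 9.1 is silent on how the two studies are combined. Whether exposure is summarised at all is unresolved between Sections 9 and 9.1 and Section 10.

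**What to change.** 1. For each Table 6 column, at least for the overview rows and serious TEAEs, add person-time from first dose in that study to first event or end of the TEAE window. Add the first-event rate per 100 patient-years with an exact Poisson 95% CI. Keep the number and percentage.
2. In SAP 9.1, define PEY separately by study and by treatment received, excluding time between the last parent dose and the first OLE dose.
3. Define All Treated Subjects in Section 5, so that numerator and denominator refer to the same people.
4. Reconcile Sections 9 and 9.1 with Section 10 on whether exposure is summarised.
5. State beside the tables that OLE subjects are those who completed the parent study, so the rates remain descriptive.

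**Cost.** No new data are needed: dose, visit and event dates from both studies are already held. The work is SAP wording plus a rate and interval in each of five columns, with time at risk derived separately for each event category. Limiting this to the overview and serious events keeps it proportionate for a discontinued program.
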